Period B: A 2-week double-blind, placebo-controlled treatment period consisting of Weeks 13 and 14 (the peri-operative period) in which subjects will continue the treatment on the first day of Weeks 13 and 14. The designated surgeon will measure the surface area of the actual surgery and record in source document. Surgery will occur during Week 13. The surgery and post-operative management (e.g., hospitalisation, surgical wound care) will be as per local practice.

[figure not shown]
Period C: A 10-week double-blind, placebo-controlled post-operative treatment period will occur from Week 15 through Week 24, during which the subject will continue the treatment assigned at Day 1 from Week 15 through Week 23. No study drug will be administered at Week 24, the final study visit. Subjects may begin commercial product (as prescribed by the subject's physician) after all Week 24 procedures have been completed.

Study procedures throughout the study are listed in [Appendix C](#). Safety and efficacy measurements will be performed throughout the study as described in Section 5.3.1.

The study visit window will be ± 3 days for the Week 2 and Week 4 visits and ± 7 days, relative to Baseline, for all study visits from Week 8 through Week 24. Surgery takes place at Week 13 after all Week 12 evaluations are completed. A subject will be brought back to the original visit schedule (calculated from the Baseline visit [Day 1]) if the subject is out of the visit window.

Subjects may discontinue adalimumab treatment at any time during study participation. Subjects that end study participation early will have a Premature Discontinuation Visit unless consent to participate is withdrawn.

Figure 1. Study Schematic

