5.2.3.4 Rescue Therapy

If the Study Investigator, with agreement of the designated surgeon, determines the subject must undergo excision of the HS surgical site prior to the Week 13 study visit window (i.e., more than 7 days prior to the scheduled Week 13 study visit) all study

procedures scheduled for Week 12 must be performed and recorded, and the subject must be discontinued from the study.

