8.1.5 Statistical Analyses of Safety

All AEs, SAEs, AEs leading to discontinuation, pre-specified AEs of special interest (AESIs) and adverse events concerning the surgical site will be collected during the study and up to approximately 70 days after the last dose of the study drug for subjects who do not elect to treat his/her HS disease with commercial adalimumab.

Safety analyses will be carried out using the Safety Population. Pretreatment AEs will be summarized. Any TEAE is defined as an event with onset or worsening after the first study drug administration and within approximately 70 days after the last study drug administration for subjects who do not elect to treat his/her HS disease with commercial adalimumab.

The number and percent of subjects experiencing treatment-emergent TEAEs will be tabulated using the Medical Dictionary for Drug Regulatory Activities (MedDRA[®]) system organ class and preferred term. Comparisons of the percentages of subjects experiencing an AE in the adalimumab group versus the placebo group will be performed

using Fisher's exact test for data collected in the entire study, and separately for Period A, Period B, and Period C. Summaries (including percentages and event per 100 patient-years) of SAEs, deaths, AEs leading to discontinuation from the study, AESIs, and adverse events concerning the surgical site will also be provided.

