location of the surgical site (i.e., axilla versus inguinal region). A subject's Hurley Stage is determined by the worst Hurley Stage (i.e., II versus III) across all affected anatomic regions. The projected size of the surgical excision established by the designated surgeon during the Screening Period (calculated from a tracing of the outer perimeter onto an acetate sheet or equivalent) will be recorded by the study physician in the CRF. On each clinical study visit day, all study procedures scheduled for that visit will be completed prior to study drug administration.

[figure not shown]
**Period B:** A 2-week double-blind, placebo-controlled treatment period consisting of Weeks 13 and 14 (the peri-operative period) in which subjects will continue the treatment on the first day of Weeks 13 and 14. The designated surgeon will measure the surface area of the actual surgery and record in source document. Surgery will occur during Week 13. The surgery and post-operative management (e.g., hospitalisation, surgical wound care) will be as per local practice.

**Period C:** A 10-week double-blind, placebo-controlled post-operative treatment period will occur from Week 15 through Week 24, during which the subject will continue the treatment assigned at Day 1 from Week 15 through Week 23. No study drug will be administered at Week 24, the final study visit. Subjects may begin commercial product (as prescribed by the subject's physician) after all Week 24 procedures have been completed.

Subjects will be contacted approximately 70 days following study drug discontinuation for an assessment of any new or ongoing AEs/SAEs, except for those subjects who continue on adalimumab not supplied in the context of the clinical trial after the end of study participation. These subjects are not required to complete the 70-day follow-up telephone call and any new AEs should be reported through the mechanism used for all post-marketing adverse experience.

The schematic of the study is shown in Figure 1. Further details regarding study procedures are located in study protocol Appendix C.

[figure not shown]
Figure 1. Study Schematic

See Section 5.2 of the protocol for information regarding eligibility criteria. Study sites and subjects will remain blinded for the duration of the study.

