### 5.0 Analysis Populations and Important Subgroups

### 5.1 Analysis Population

The Intent-to-Treat (ITT) Population is defined as all subjects who randomised at the Baseline visit. The ITT Population will be used for the efficacy analysis. Of note, the surgery-related endpoints during Periods B and C will be analysed among the subjects who undergo surgery. Subjects in the ITT population will be analysed by treatment group as randomised.

In order to evaluate the impact of major protocol deviations on the primary efficacy endpoints, additional sensitivity analyses may be performed on a Per-protocol Population, which excludes subjects with major protocol deviations that potentially affect the primary efficacy endpoints. If it is decided that this analysis should be performed, the criteria for exclusion of subjects from the Per-protocol Population will be fully defined in the classification plan and the exclusion of subjects from the Per-protocol Population will be finalized before blind break and before the database lock.

The Safety Population is defined as all subjects who are in the ITT Population and receive at least one dose of study drug. The Safety Population in each period will be used for safety analysis. Of note, the surgery-related safety endpoints during Periods B and C will be analysed among the subjects who undergo surgery. Subjects in the Safety Population will be analysed by treatment group as treated.

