### 7.2 Analysis of Adverse Events

Treatment-emergent adverse events (TEAEs) are defined as any event with an onset that is after the first dose of study drug and with an onset date within 70 days after the last dose of study drug in the analysis period, or prior to the first dose in the subsequent period for subjects who entered in to the subsequent period.

Pre-treatment AEs will be summarized separately.

All TEAEs, serious adverse events (SAEs), AEs leading to discontinuation and AEs of Safety Interest will be summarized. The number and percentages of subjects experiencing TEAE will be tabulated using the Medical Dictionary for Drug Regulatory Activities (MedDRA®) system organ class and preferred term.

Summaries (including percentages and event per 100 patient-year) of SAEs, deaths, AEs leading to discontinuation, and AEs of Special Interest will be provided as well. No statistical tests will be performed.

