### 7.5 Safety Subgroup Analysis

The AE overview and AE by SOC and PT in each period will also be analysed with respect to the following Baseline characteristics. The subgroups are:

- Current smoking status at Baseline (yes, no)
- HbA1c (< 7%,  $\ge 7\%$ )
- BMI (< 40, > 40)
- Prior HS surgery history (yes, no)

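### By-period adverse event tables: SAP 7.2 gives subjects who stop in Period A or B a different counting window from subjects who continue, so percentages compare unequal follow-up and Period A can include events after withdrawal or early excision

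*SAP*

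**What the plan says.** SAP 7.2 defines a treatment-emergent event as one with onset after the first dose and "within 70 days after the last dose of study drug in the analysis period, or prior to the first dose in the subsequent period". The earlier cut-off is reserved "for subjects who entered in to the subsequent period". The first Period B dose is fixed by SAP 4.2.1, where subjects continue "the treatment on the first day of Weeks 13 and 14". Planned surgery belongs to Period B: "Surgery will occur during Week 13" (Protocol 5.1.1).

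A subject whose surgical site has to be excised well before Week 13 completes the Week 12 procedures "and the subject must be discontinued from the study" (Protocol 5.2.3.4). Protocol 5.2.3.2 likewise requires discontinuation after more than two lesion interventions in Period A. Protocol 6.1.4 collects adverse events for about 70 days after stopping, or until commercial adalimumab starts. Protocol 6.1.1.1 says the need for early surgery is not itself an adverse event, but it does not exempt later events.

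By-period tables are called for in three places. Protocol 8.1.5 compares adverse event percentages "for data collected in the entire study, and separately for Period A, Period B, and Period C". SAP 5.1 states "The Safety Population in each period will be used for safety analysis". SAP 7.5 states "The AE overview and AE by SOC and PT in each period will also be analysed". Against these, SAP 8.0 justifies one edit by saying that safety has a single study period.

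SAP 7.2 gives the overall table by system organ class and preferred term as numbers and percentages. It names rates per 100 patient-years only for serious events, deaths, events leading to discontinuation and events of special interest.

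**The concern.** The length of the Period A window depends on something that happens after randomisation: whether the subject goes on to Period B. The same holds for Period B, since only subjects who enter Period C are cut at the first Period C dose. A percentage of subjects with an event depends on how long each subject is watched. If the arms differ in dropout, they are compared over different average follow-up.

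The content of the extra time also matters. For a subject who stops, the tail is time off study drug. For a subject whose site was excised early, it is post-operative time. A continuer's post-operative time falls in Period B or later. Protocol 5.6.1 says the design allows safety to be compared both before and after excisional surgery, and a Period A table with mixed content blurs that contrast.

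**Working it through.** **Plan's own figure.** The documents give no adverse event rate, dropout rate or per-period safety figure, so there is none to reproduce. The check rests on the window rule.

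**Step 1: Period A windows.** Inputs: Period A doses at Weeks 0, 2 and 4 to 12 (Protocol 5.5.1); first Period B dose on the first day of Week 13 (SAP 4.2.1); 70-day tail (SAP 7.2). In days from first dose:

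- Continuer: 7 × 13 = 91.
- Stopper: 7 × (week of last dose) + 70.

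| Last dose | Window (days) | Minus 91 |
|---|---|---|
| Week 0 | 70 | −21 |
| Week 2 | 84 | −7 |
| Week 4 | 98 | +7 |
| Week 8 | 126 | +35 |
| Week 12 | 154 | +63 |

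The mean over the 11 possible dose weeks is 1288/11 = 117 days. The tail is 70/154 = 45% of the window at Week 12 and all of it at Week 0. These are maxima, because collection ends when commercial adalimumab starts.

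**Step 2: Periods B and C.** A subject entering Period C leaves Period B at 7 × 15 = 105 days. A subject whose last dose is at Week 13 or 14 stays until up to 91 + 70 = 161 or 98 + 70 = 168 days. Nobody enters a period after C, so all Period C subjects follow the 70-day rule alone.

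**Step 3: illustrative size, last doses spread evenly.** Assumptions, none from the documents: the same constant hazard r (first events per patient-year) in both arms; last dose of stoppers spread evenly over the 11 dose weeks; Period A dropout 5% v 15%, or 5% v 25%.

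- Risk over d days = 1 − exp(−r × d/365.25).
- Spurious arm difference = (difference in dropout) × (mean stopper risk − continuer risk).

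| r | Continuer | Stopper | 5% v 15% | 5% v 25% |
|---|---|---|---|---|
| 0.2 | 4.9% | 6.2% | 0.13 | 0.27 |
| 0.5 | 11.7% | 14.8% | 0.30 | 0.61 |
| 1.0 | 22.1% | 27.3% | 0.52 | 1.04 |
| 2.0 | 39.2% | 46.8% | 0.76 | 1.52 |

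The last two columns are percentage points, higher in the arm with more dropout. With equal dropout the difference is 0. If the hazard is assumed to triple after stopping, 5% v 15% gives 0.83, 1.79, 2.84 and 3.61 points.

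**Step 4: second illustration, all stoppers at Week 8.** Assume 40% to 60% of subjects have an event by 12 weeks, with weekly hazard h = −ln(1 − p)/12, and dropout 5% v 15% or 8% v 20%. Continuers have 13 weeks and stoppers 18. For p = 0.5, the risks are 1 − exp(−13h) = 52.8% and 1 − exp(−18h) = 64.6%. The difference is 0.10 × 11.8 = 1.2 points, or 0.12 × 11.8 = 1.4. Over the whole range it is 1.1 to 1.4 points, and 2.5 to 3.3 if the hazard doubles after stopping.

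**Step 5: two simple repairs tested.**

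- *Cut percentages at early excision.* If all the Week 8 stoppers in Step 4 are excised then, they have 8 weeks against 13. For p = 0.5 the risk is 37.0% against 52.8%, so the difference is 0.10 × (37.0 − 52.8) = −1.6 points. The range is −1.4 to −2.1: opposite in sign and larger than the error being repaired.
- *Cap everyone at Day 91.* In Step 3 with r = 0.5 and 5% v 15%, 0.30 becomes −0.03 with equal hazards, but 1.79 falls only to 0.91 with a tripled hazard. The cap also drops continuers' events between Day 91 and a late first Period B dose. Late doses are possible: visits may be up to 7 days late (Protocol 5.1.1), missed injections may be taken late (5.5.4), and dosing may be interrupted for infection (6.1.7).

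**The case against.** The strongest objection is that the by-period tables may not exist. SAP 8.0 speaks of one safety period. On that reading there is no subsequent period, every subject has the same 70-day rule, and the problem disappears. This stands as a condition. It does not dispose of the point, because Protocol 8.1.5 and SAP 5.1 and 7.5 all refer to separate periods, and the continuer clause in SAP 7.2 does nothing if there is only one. The log entry is used here only as evidence of intent.

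The second objection is size. With equal hazards, about 1 point is one subject in 100 per arm. The standard error of a difference at 40% to 60% incidence is about √(2 × 0.5 × 0.5/100) = 7 points. SAP 7.2 plans no tests on adverse events, although Protocol 8.1.5 plans Fisher's exact test. The gravest categories already have patient-year rates. All of this stands and keeps the point modest.

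A reader might go further and infer that the rule makes adalimumab look safer before surgery, because early excision and excess interventions would be commoner on placebo. The documents do not support that. They give no dropout rate by arm. Adverse events, infections and laboratory abnormalities also lead to withdrawal (Protocol 5.4.1) and could fall more on adalimumab. Stopping at Week 0 or 2 shortens the window. Subjects who leave with uncontrolled disease may start commercial adalimumab, which ends their tail.

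**Conclusion.** The point holds where adverse event tables are produced by period. The Period A and Period B windows then depend on whether the subject continues, and Period A percentages can include events after withdrawal or early excision. That follows from the text alone.

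Direction and size are unknown. Under the assumed dropout and event rates, the artefact is about 0.1 to 1.5 points with equal hazards. It is larger, about 0.8 to 3.6 points in the cases shown, only if event rates are assumed to double or triple after stopping. No document supplies such a multiplier.

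A reader might also extend the point to Period C or to the overall safety comparison. Neither follows: Period C has no later period, and the whole-study table uses one rule for everyone. This is a low-cost improvement to how the period tables are read, and no threat to the trial's main safety comparison.

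**What to change.** 1. State in one place how many safety analysis periods there are, and bring Protocol 8.1.5 and SAP 5.1, 7.2, 7.5 and 8.0 into line. If there is one, remove the continuer clause from SAP 7.2.
2. If period tables are kept, report events per 100 patient-years for all treatment-emergent events in them, using each subject's actual time in the window. Show events with onset after discontinuation, or after early excision of the surgical site, in a separate row or table and not as pre-surgery events.
3. Keep the 70-day rule for the whole-study table.

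Do not compare bare percentages with the window truncated at excision, and do not impose a fixed Day 91 cut, for the reasons in Step 5 of the working. Patient-year rates remove the unequal-length problem when hazards are constant. The separate display deals with event rates that change after stopping.

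The cost is one extra table, some programming and a short SAP edit. The dose, surgery and event dates needed are part of the planned data.

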Adalimumab trough serum concentrations will be summarized at each time point using descriptive statistics. In addition, pharmacokinetic-pharmacodynamic (PK-PD) model-based analyses will be performed to evaluate adalimumab PK and exposure-response relationships.

Statistical Methods (Continued):

Safety:

All adverse events (AE), serious adverse events (SAE), AEs leading to discontinuation, and pre-specified AEs of special interest and adverse events concerning the surgical site will be collected during the study and up to approximately 70 days after the last dose of study drug, for subjects who do not elect to treat his/her HS disease with commercial adalimumab.

Safety analyses will be carried out using the Safety Population, which consists of subjects who received at least one dose of study drug. Pretreatment AEs will be summarized. A treatment-emergent AE (TEAE) is defined as an event with onset or worsening after the first study drug injection and within approximately 70 days after the last study drug injection, for subjects who do not elect to treat his/her HS disease with commercial adalimumab.

The number and percent of subjects experiencing TEAEs will be tabulated using the Medical Dictionary for Drug Regulatory Activities (MedDRA[®]) system organ class and preferred term. Comparisons of the percentages of subjects experiencing an AE in the adalimumab group versus the placebo group will be performed using Fisher's exact test for data collected in the entire study, and separately for Period A, Period B, and Period C. Summaries (including percentages and event per 100 patient-years) of SAEs, deaths, AEs leading to discontinuation from the study, and pre-specified AEs of special interest will be provided as well. Mean change in laboratory variables and vital sign variables at each visit will be summarized; the comparison between the adalimumab treatment group and placebo group will be carried out using a one-way ANOVA.

Immunogenicity:

Anti-Adalimumab Antibody (AAA) will be evaluated for each subject and rates of AAA positive will be calculated. As appropriate, the effect on adalimumab PK, efficacy, and treatment-emergent adverse events may be evaluated.

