6.1.1.3 Adverse Events of Special Interest

Adverse events of special interest as defined in [Table 3](#), and adverse events concerning the surgical site will be collected and analysed.

Table 3. Adverse Events of Special Interest

Serious and nonserious opportunistic infections, including the following bacterial, fungal, viral and parasitic infections: Aspergillus, Blastomyces, Candida, Coccidioides, Cryptococcal, Cytomegalovirus, Histoplasma, Listeria, Nocardia, Paracoccidioides, Pneumocystis, Toxoplasma, Tuberculosis, Herpes, Bacillary angiomatosis, Mucormycosis, Progressive Vaccinia, Zygomycosis, BK virus, and JC virus
Lymphoma
Hepatosplenic T-cell lymphoma
Leukemia
Non-melanoma skin cancer (NMSC)
Other malignancies (except lymphoma, leukemia and NMSC)
Immune reactions including lupus, lupus-like reactions, and severe allergic reactions
Congestive heart failure (CHF)
Cerebrovascular accident (CVA)
Myocardial infarction (MI)
CNS demyelinating disorders (including MS and Guillain-Barré syndrome)
Hepatic events that are serious or lead to permanent discontinuation of study drug (e.g., persistent liver function test abnormalities, acute liver failure and other serious hepatic events)
Hematologic events that are serious or lead to permanent discontinuation of study drug (e.g., aplastic anemia, granulocytopenia, Granulocyte Maturation Arrest, leukopenia, neutropenia, nancytopenia and thrombocytopenia)
Worsening of Psoriasis
Vasculitis
Diverticulitis
Intestinal perforation

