- Analysis of imputed data sets. A Cochran-Mantel-Haenszel (CMH) test using Wilson-Hilferty transformation, stratified by stratification factors, will be used to analyse HiSCR response rates in each imputed dataset.
- Synthesis of imputation and analysis results. SAS PROC MIANALYZE will be used to generate the final inferences of the risk difference between treatment groups.

The 3rd and 4th ranked secondary endpoints will only be analysed by OC approach. For subjects whose surgery is no longer needed due to HS improvement, the actual surgical

area would be treated as 0 and the type of surgery would be treated as a less-extensive surgery. Subjects who discontinued before surgery due to AE of worsening in HS, or exceeding protocol specified number of lesion interventions, or planned HS surgery performed prior to Week 13, will be forced as no change in the planned surgical area and no less-extensive surgery.

In all methods of handling missing data, efficacy assessments observed on or before the planned surgery cannot be used to impute missing values for post-surgery visits, except for the lesion count on body regions other than the surgical site.

[figure not shown]
Lesions that receive protocol-allowed intervention (e.g., contained within the excised surgical specimen, protocol-allowed minor interventions including incision and drainage) will be counted as permanently present from the date of the intervention.

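### SAP 7.2 rules out the adverse-event comparisons that Protocol 8.1.5 plans, and does not list the surgical-site adverse-event summary that the protocol promises

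*SAP*

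**What the plan says.** **Tests.** The protocol synopsis states that "Comparisons of the percentages of subjects experiencing an AE in the adalimumab group versus the placebo group will be performed". Protocol 8.1.5 plans the same comparison, using Fisher's "exact test for data collected in the entire study, and separately for Period A, Period B, and Period C". SAP 7.2 plans counts, percentages and rates per 100 patient-years, and ends: "No statistical tests will be performed".

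**Surgical-site events.** Protocol 6.1.1.3 treats these as a group beside the AEs of special interest (AESIs) in Table 3, "and adverse events concerning the surgical site will be collected and analysed". Protocol 8.1.5 promises percentages and events per 100 patient-years for SAEs, deaths, discontinuations, "AESIs, and adverse events concerning the surgical site will also be provided". The matching list in SAP 7.2 stops at discontinuations "and AEs of Special Interest will be provided as well". SAP 5.1 adds that "the surgery-related safety endpoints during Periods B and C will be analysed among the subjects who undergo surgery", but does not say what those endpoints are.

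**Periods.** SAP 5.1, 7.2 and 7.5 use period wording for safety. The version 3 entry in SAP 8.0 gives as a rationale that safety has a single study period.

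**Where details belong.** Protocol 8.1 leaves the complete analysis details to the SAP. SAP 3.0 calls itself high-level and refers further conventions to a supplement, which is not among the documents reviewed.

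**The concern.** Protocol 4.1 and SAP 4.1 both make safety through the perioperative period and after surgery a secondary objective. Protocol 5.6.1 justifies the placebo control partly by the safety comparison it allows before and after excision, and Protocol 3.6 presents the trial as the first randomised study of peri-surgical adalimumab. Surgical-site events are therefore the safety outcome most specific to this trial.

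If SAP 7.2 is followed as written, such events would appear under whatever system organ class and preferred term each was coded to, and the combined summary that the protocol promises would not be required. With no definition fixed before unblinding, any grouping made later could be questioned as chosen after the results were seen. Separately, two governing documents give opposite instructions on AE tests, so whoever programs the tables must depart from one of them.

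**Working it through.** **1. Compare the texts.**

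| Item | Protocol | SAP |
|---|---|---|
| Between-arm AE tests | Fisher's exact: whole study and Periods A, B, C (1.2, 8.1.5) | None (7.2) |
| Surgical-site AE summary | Promised, separate from AESIs (6.1.1.3, 8.1.5) | Not listed (7.2) |
| Definition of surgical-site AE | None; Table 3 covers AESIs only | None |
| Analysis set | Operated subjects (8.1.1) | Operated subjects (5.1) |
| Risk difference with CI for AEs | None | None |

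The change list in SAP 8.0 mentions neither the Fisher tests nor the surgical-site summary.

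**2. Analysis set.** SAP 4.7 makes provision "For subjects whose surgery is no longer needed due to HS improvement". It also names subjects who leave before surgery for worsening HS, for too many lesion interventions, or because the planned surgery was done before Week 13. Whether a subject enters the operated set is thus decided after randomisation and may depend on treatment. An operated-only comparison is natural for wound events, but it is not a fully randomised one.

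**3. Precision.** Neither document states a power or precision figure for safety, so there is none to reproduce. The inputs below are assumptions: 80 to 100 operated per arm (100 per arm is the planned enrolment) and event rates of 5% to 30%.

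For x events in n subjects, p = x/n and z = 1.96, the Wilson limits are

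(l, u) = [p + z²/2n ± z√(p(1−p)/n + z²/4n²)] / (1 + z²/n).

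The Newcombe interval for d = p₁ − p₂ runs from d − √((p₁−l₁)² + (u₂−p₂)²) to d + √((u₁−p₁)² + (p₂−l₂)²).

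Equal rates, 9/90 in each arm: the Wilson limits are 5.35% and 17.92%, so the half-width is √(4.65² + 7.92²) = √84.35 = 9.2 points. Other cases, in points:

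| Operated per arm | 5% | 10% | 20% | 30% |
|---|---|---|---|---|
| 80 | 7.8 | 9.8 | 12.4 | 14.0 |
| 90 | – | 9.2 | 11.7 | 13.2 |
| 100 | 6.8 | 8.7 | 11.1 | 12.6 |

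(5% of 90 is not a whole number of events.)

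Unequal rates, 18/90 against 9/90: the Wilson limits are 13.04% to 29.41% and 5.35% to 17.92%.
- Lower: 10 − √(6.96² + 7.92²) = 10 − 10.54 = −0.5.
- Upper: 10 + √(9.41² + 4.65²) = 10 + 10.50 = 20.5.

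The result is 10.0 points (−0.5 to 20.5).

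**4. What Fisher's test alone would add.** Exact power is the sum of Bin(i; n, p₁)·Bin(j; n, p₂) over all tables with two-sided P ≤ 0.05. With 80, 90 and 100 per arm it is 14%, 17% and 19% for 10% against 5%, and 35%, 40% and 44% for 20% against 10%. A non-significant result would therefore say little, whereas an interval shows how large an excess remains compatible with the data.

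**5. Denominator, by example.** Assume 100 treated per arm, 80 against 95 operated, events in 20% of operated subjects (16 and 19), and no event observed in the others. Operated only: 16/80 − 19/95 = 0.0 (−11.7 to 12.1). All treated: 16/100 − 19/100 = −3.0 (−13.6 to 7.6). The shift comes entirely from the assumed difference in how many were operated, which is why those numbers and the reasons need to be shown by arm.

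**The case against.** Several points on the other side stand. Reporting AEs descriptively is a defensible choice, and by the figures above the Fisher tests would have low power, so little inferential value is lost without them. The protocol already commits to the surgical-site summary, and SAP 5.1 sets its population. The missing definition is a gap in the protocol as much as in the SAP. SAP 7.2 also mentions AEs of safety interest as well as AEs of special interest; this may be a slip or a wider group. An all-treated comparison mixes the avoidance of surgery, part of the fourth ranked efficacy endpoint, into a safety contrast, so it can only be supportive.

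Some stronger readings are tempting, but the documents do not support them:
- **That no surgical-site table will be produced.** The supplement may contain a term list or table list. What can be said is that SAP 7.2 does not require the table.
- **That the missing risk difference and interval breaks a commitment.** Neither document promises them for AEs.
- **That the tests were removed late, or with knowledge of results.** The change list is silent, which also fits the sentence having been there from the outset. SAP 8.0 places the version 3 changes before database lock and unblinding.
- **That subjects without surgery can simply be counted as event-free.** The surgical site is designated at entry, so an event there is possible without an operation. Some of these subjects leave early, and SAP 7.1 says missing safety data are not imputed.

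The supplement, as SAP 3.0 describes it, guides programming. It would not by itself resolve a conflict between the protocol and SAP 7.2.

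**Conclusion.** The concern holds on the text in two respects: opposite instructions on AE tests, with no explanation, and a promised surgical-site summary that SAP 7.2 omits and neither document defines. It should be corrected because it touches a secondary objective and the fix is cheap. Its reach is limited: per-arm descriptive AE tables remain, and no confirmatory inference changes.

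The interval is an improvement and would be wide: about 7 to 14 points either side at equal rates of 5% to 30% with 80 to 100 operated per arm. These rates and numbers operated are assumptions; the textual finding does not depend on them. Confidence is medium because the supplement was not seen.

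**What to change.** In SAP 7.2:

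1. Add the surgical-site AE summary promised in Protocol 8.1.5, by arm, with percentages and events per 100 patient-years, using a term list or eCRF flag fixed before unblinding. As an improvement, add the risk difference with a Newcombe 95% confidence interval.
2. Present it among operated subjects, as SAP 5.1 states. As a supportive table, show it among all treated subjects using observed events only, with no imputed absence of events, and give the number not operated and the reasons by arm. State where subjects whose planned surgery took place before Week 13 are placed.
3. Reconcile Protocol 8.1.5 and the synopsis with SAP 7.2 on the Fisher tests: either restore them, or amend the protocol and give the reason.
4. Before fixing any by-period tables, settle how the period wording in Protocol 8.1.5 and SAP 5.1, 7.2 and 7.5 fits with the single safety period named in SAP 8.0.

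The cost is some SAP wording (with a protocol amendment if the tests stay out), one term list or flag, and a few tables from AE data already collected. The downside is that the intervals will be wide, and readers should be told so.
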